## II. Consolidation

Assessment	Baseline - Consolidation 1-4	On Treatment - Consolidation 1-4
Day	First day of HiDAC consolidation	First day of crenolanib
Prior/Concomitant medications and significant non-drug therapies	X	X
Physical examination with ECOG PS	X	X
EKG a		X*
Vitals and Weight	X	X
Assessment of adverse events, toxicities	X	X
Hematology (CBC with differential) c	X	X
Serum Chemistries (CMP with bilirubin, ALT/AST and creatinine) c	X	X +
Urine or serum pregnancy test		Every 6 months while patient is on study
Blood collections for PK and correlative sciences b		X*
Bone marrow biopsy and aspirate d		Per SOC

**Key:**

a EKG is to be performed 2 hours ( $\pm$  30 minutes) post first dose of crenolanib during Consolidation 1

b Blood samples for translation research (including PK analysis) should be collected as defined in Section 11.

\* EKG and blood for PK will only be collected during Consolidation 1

c CBC with differential and CMP should be performed at least weekly while patients are receiving crenolanib during induction. Additional labs may be performed per SOC, for safety, the sponsor may request additional labs done per SOC be captured

d Prior to initiation of crenolanib (within 24 hours of first dose) following HiDAC consolidation, bilirubin, ALT and AST must meet eligibility criteria as depicted in section 1 treatment overview

d Bone marrow biopsy and aspirate performed should have FLT3 testing and mutational status if available

Per SOC: Physician visits (with ECOG PS, vitals, weight, concomitant medication assessment and adverse events assessments) should be performed as per SOC while patients are receiving crenolanib during induction. At a minimum adverse events and concomitant medications should be reported to the sponsor (per EDC) monthly.

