## 1. OVERVIEW OF THE TREATMENT PLAN

### INDUCTION

[figure not shown]

\* Daunorubicin dose:

- 90 mg/m^2: Age < 60
- 60 mg/m^2: Age  $\geq$  60 or for patients who are <60 and receiving a second cycle of induction (per physician's discretion)

- Crenolanib starts approximately 24-48 hours after completion of Cytarabine (+7-day window). **Normal total bilirubin and ALT and AST  $\leq$  2.0x ULN are required within 24 hours prior to crenolanib commencement. Crenolanib can be delayed until these criteria are met.** (If crenolanib will be delayed longer day 16, a discussion with PI and sponsor should be conducted to determine the best options for the patient)
- On first day of crenolanib, only one 100 mg dose given; from second day on, all three doses given (100 mg TID)
- A total of two cycles of induction will be allowed.
- Crenolanib should be held 72 hours prior to subsequent chemotherapy

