#### 5.5. Clinical studies of crenolanib in AML

##### 5.5.1. Clinical summary of crenolanib in relapsed/refractory FLT3 mutated AML

Crenolanib has been studied in relapsed/refractory FLT3 mutant AML (NCT01522469, NCT01657682). Crenolanib was administered as single-agent in 69 patients with relapsed/refractory FLT3 mutated AML in two clinical trials, NCT01522469/ARO-004 and NCT01657682/ARO-005. Encouraging single-agent activity, safety and PK was observed with crenolanib in this patient population. Amongst 18 evaluable who had relapsed AML patients after chemotherapy or allogeneic stem cell transplant (but who had not received prior FLT3 inhibitors), crenolanib therapy resulted in an overall response rate of 50% (39% CR and 11% PR). Median overall survival was almost eight months (234 days). The overall response to crenolanib monotherapy was 31% in 36 patients who progressed after a median of three prior regimens (including chemotherapy and FLT3 inhibitors like sorafenib, midostaurin and quizartinib). Crenolanib had a half-life of 7.5hrs and no crenolanib accumulation seen with repeated dosing. Common adverse events (AEs) included nausea/vomiting, transaminitis and fluid retention (majority Grade 1/2) and only 2 patients discontinued crenolanib due to related AEs (fatigue and nausea). No patient acquired a secondary FLT3 mutation at the time of relapse following crenolanib.

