**Figure 7 Representative PIA analysis of patient plasma samples after taking crenolanib single agent.**

The study by Robert J. et al. in 16 leukemia patients showed that the major metabolites of idarubicin or daunorubicin were the 13-dihydroderivative of each drug, idarubicinol or daunorubicinol. The elimination half-life of idarubicinol was two times higher than that of daunorubicinol (80.7 h versus 37.3 h). [6] During 7+3 induction in this protocol, idarubicin or daunorubicin will be administered on days 1, 2, and 3. By the time crenolanib is started (Day 9), idarubicinol level should have declined by 75% (2 half-lives) and daunorubicinol levels will have dropped by 93.5% (4 half-lives). Crenolanib will be discontinued 3 days (9 half-lives) prior to initiation of subsequent chemotherapy.

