## 8. TREATMENT PLAN

### 8.1. Summary of Treatment

This is a non-randomized, open label, phase II study enrolling newly diagnosed AML subjects with FLT3 activating mutations. Along with chemotherapy, subjects will be treated with crenolanib divided in three divided doses (preferably every 8 h) continuously until they fulfill one of the criteria for study discontinuation (see Section 7.4).

Study subjects, nursing or research staff will complete documentation (i.e patient diary) during induction and first cycle of consolidation to record the date, time and amount (number of tablets) of crenolanib taken and when taken relative to food. While study subjects are hospitalized, medical records, such as Medication Administration Record, may be used to enter data requested. Once subject is discharged from the hospital, they must submit the crenolanib administration documentation as required during induction 1 (and 2 if applicable), consolidation 1 (Appendix III). All subjects will be assessed for efficacy and toxicity.

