### 8.2.2. Consolidation

Therapy with crenolanib will be held for 72 hours prior to the start of the first dose of cytarabine given for consolidation. Crenolanib treatment should be continued during the period of marrow recovery.

Subjects on both cohorts A and B may have up to 4 consolidation courses with:

- High dose cytarabine (HiDAC) given as 3 g/m^2 ( $<$ 60 years old) or 1 g/m^2 (for  $\geq$ 60) intravenously over 3 h every twelve hours on days 1, 3, 5 (total of 6 doses).

Crenolanib will start approximately 24-48 hours after completion of cytarabine (+7 day window). Adequate liver function including normal total bilirubin ALT and AST  $\leq$ 2.0x ULN are required within 24 hours prior to crenolanib commencement. Crenolanib can be delayed until this criterion is met (If crenolanib will be delayed longer day 14, a discussion with PI and sponsor should be conducted to determine the best options for the patient).

- Dose of crenolanib will be the same as that given in induction(s).
- Dose modification of crenolanib is allowed based on treating physician discretion according to Section 8.4 of this protocol.

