#### **14.10. Overdose**

To date there have been no instances of patients who were inadvertently overdosed. Clinical studies have shown an apparent crenolanib half-life of approximately 8 hours. It is anticipated that

crenolanib would be metabolized and excreted within 5 half-lives of the drug. No specific antidote exists for the treatment of crenolanib overdose. Investigators will be advised that any patient who receives a higher dose than that intended should be monitored closely, managed with appropriate supportive care and followed up expectantly.

If an overdose occurs in the course of the study, then investigators or other site personnel must inform the sponsor immediately, or **no later than 24 hours** of when he/she becomes aware of it.

Such overdoses should be recorded as follows:

- An overdose with associated AEs/SAEs is recorded as the AE diagnosis/symptoms on the relevant AE/SAE modules in the eCRF.
- An overdose with no associated symptoms should be documented on the eCRF module for dosing of study drug.

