**Key:**

a count recovery is defined as : ANC  $\geq$ 1000 and platelets  $\geq$ 100,000

a Screening assessments should be performed within 28 days of enrollment with the following exceptions: CBC, CMP and pregnancy test (when applicable) should be performed within 7 days of enrollment, bone marrow biopsy and aspirate and evaluation of FLT3 and other mutational status should be performed within 21 days of enrollment

\* If screening assessments were performed while patient was receiving induction chemotherapy, the following assessments performed prior to starting induction, if done per standard of care, may be requested by the sponsor: CBC with differential, CMP with bilirubin, ALT/AST, and bone marrow biopsy and aspiration

b EKG is to be performed pre-dose crenolanib (baseline on the first day of crenolanib) as well as 2 hours ( $\pm$  30 minutes) post first dose of crenolanib during Induction 1

c Peripheral and whole blood samples for translation research (including PK analysis) should be collected as defined in Section 11.

\*\* EKG, Peripheral blood for PK analysis and Whole blood sample will only be collected during Induction 1

d CBC with differential and CMP should be performed at least weekly while patients are receiving crenolanib during induction. Additional labs may be performed per SOC, for safety, the sponsor may request additional labs done per SOC be captured

e Bone marrow biopsy and aspirate performed on day 14-28 should have FLT3 testing and mutational status if available

Per SOC: Physician visits (with ECOG PS, vitals, weight, concomitant medication assessment and adverse events assessments) should be performed as per SOC while patients are receiving crenolanib during induction. At a minimum adverse events and concomitant medications should be reported to the sponsor (per EDC) monthly.

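### Both scheduled post-dose EKGs follow a first dose given from essentially zero drug, so no scheduled EKG informs on continuous TID dosing

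*Combined protocol and SAP*

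**What the plan says.** **EKG schedule.** For Induction 1, the key to Appendix IV part I states: "EKG is to be performed pre-dose crenolanib (baseline on the first day of crenolanib) as well as 2 hours" after the first dose. Section 10.2 item 2 gives the same two time points. For consolidation, Section 10.3 item 2a and key a of Appendix IV part II place one EKG 2 h (± 30 minutes) "post first dose of crenolanib during Consolidation 1". The two keys confine EKGs to Induction 1 and Consolidation 1. None is listed at screening (10.1), in maintenance (Appendix IV part III) or at progression or completion (10.4).

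**Washout before consolidation.** Section 8.2.2 states: "Therapy with crenolanib will be held for 72 hours prior to the start of the first dose of cytarabine given for consolidation". Section 5.8 expresses the same interval in half-lives: "Crenolanib will be discontinued 3 days (9 half-lives) prior to initiation of subsequent chemotherapy". HiDAC is then given on days 1, 3 and 5, and crenolanib restarts about 24 to 48 h after the last cytarabine, with a further 7-day window.

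**Kinetics.** Section 5.5.1 states: "Crenolanib had a half-life of 7.5hrs and no crenolanib accumulation seen with repeated dosing". Section 3.1 says the same. Section 14.10 gives an "apparent crenolanib half-life of approximately 8 hours". Section 8.1 asks for three doses a day, preferably 8 h apart. Section 5.8 treats steady state as reached by Day 15, and Section 11 takes PK samples on Day 15 of crenolanib in Induction 1, with no EKG attached.

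**The concern.** An EKG 2 h after a first dose shows the response to one dose. It cannot show the response to repeated dosing, whatever the accumulation ratio is. The second post-dose EKG could have filled that gap. Instead it is placed after a washout that the protocol itself counts as 9 half-lives, so it largely repeats the first condition.

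Patients then take the drug continuously, possibly for many months, after an anthracycline and with CYP3A4 inhibitors allowed with caution (8.6, Appendix VI). The trial has a primary safety objective, but its scheduled EKGs would not support a statement about EKG findings under sustained dosing.

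The half-life and the dosing interval also appear to contradict the statement that no accumulation was seen. A reader therefore cannot tell from the protocol how far first-dose exposure falls short of steady-state exposure.

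**Working it through.** **Inputs.** Half-life t = 7.5 h (3.1, 5.5.1) or about 8 h (14.10). Dosing interval τ = 8 h, stated as a preference (8.1). Hold of 72 h before cytarabine (8.2.2). Linear one-compartment kinetics are assumed; the documents do not establish them.

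**1. The protocol's own figure.** Washout in half-lives = 72 / t.
- t = 8 h: 72 / 8 = 9.0, which reproduces the stated 9.
- t = 7.5 h: 72 / 7.5 = 9.6.

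**2. Drug remaining at the Consolidation 1 EKG.** Fraction remaining after the hold alone = 0.5^(72/t).
- t = 7.5 h: 0.13%.
- t = 8 h: 0.20%.

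The restart is later still. The sixth cytarabine dose begins 4 days and 12 h after the first and runs for 3 h. The shortest gap is therefore about 72 + 96 + 12 + 3 + 24 = 207 h, or 8.6 days. That is 207 / 8 = 25.9 half-lives (27.6 at 7.5 h), so nothing measurable is carried over.

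**3. Implied accumulation.** R = 1 / (1 − 2^(−τ/t)).

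| τ | t = 7.5 h | t = 8 h |
|---|---|---|
| 6 h | 2.35 | 2.47 |
| 8 h | 1.91 | 2.00 |
| 10 h | 1.66 | 1.73 |

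The documents give no absorption rate. If first-order absorption of 0.5 to 2 per hour is assumed, the steady-state to first-dose ratio of concentrations at 2 h is about 1.9 to 2.8 for τ = 8 h.

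**4. Effect of dose reduction.** R applies at an unchanged dose. Against a first dose of 100 mg, the ratio at the Table 4 levels is:
- 80 mg TID: 0.8 × 1.91 to 0.8 × 2.00 = 1.53 to 1.60.
- 60 mg TID: 0.6 × 1.91 to 0.6 × 2.00 = 1.15 to 1.20.

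**5. Time to reach steady state.** 95% of steady state takes t × log2(20) = 32.4 h (t = 7.5 h) to 34.6 h (t = 8 h) of regular dosing. A reading 2 h after a first dose cannot reflect it; a reading about a week into uninterrupted dosing can.

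**6. The conflict.** No accumulation would mean R = 1. Under linear kinetics with these half-lives, R exceeds 1 at every interval in the table. Either the half-life or the accumulation statement needs correction or explanation. The phrase may, for example, mean no accumulation beyond what was predicted, but the protocol does not say so.

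**The case against.** The strongest objection is to the twofold figure. It is modelled, and the only observation the protocol reports points the other way. The half-life is called apparent. If it is a terminal half-life after a multi-phase decline, true accumulation would be lower. The 8 h interval is only preferred, and dose reductions shrink the ratio. The day-1 profile is in Figure 6, which was not available for this check. All of this stands: a reader might infer that steady-state exposure is expected to be double, but the documents support that only as an implication of linear kinetics.

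Two other strong readings also go too far:
- **That EKGs are the only scheduled cardiac safety measurement.** Physical examination and vital signs are scheduled in every phase, adverse events after the first dose are reported, significant cardiac disease is excluded at entry, and unscheduled EKGs are not barred.
- **That a normal first-dose EKG would be taken as proof of cardiac safety at 100 mg TID.** Nothing in the documents says this. EKG is not an endpoint and is not among the safety outcomes summarised under 13.8. The protocol names no QT or arrhythmia signal.

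The lead-in to Section 10.3 item 2 refers generally to EKGs in induction and consolidation and might suggest wider monitoring. Its only item is the Consolidation 1 first-dose EKG, and both Appendix IV keys are restrictive, so it adds no time point.

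None of this answers the timing point. Even with R = 1, no scheduled EKG is taken under repeated dosing.

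**Conclusion.** The point holds as a gap in measurement timing. Two post-dose EKGs are scheduled, both after a first dose from essentially zero drug, and none during continuous dosing. This rests on the schedule text alone and needs no kinetic assumption.

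The size of the exposure difference is conditional: 1.9 to 2.0 times at 8 h spacing and an unchanged dose, and about 1.7 to 2.5 times across 10 h to 6 h spacing, under linear kinetics. It should be presented as implied, together with the conflicting no-accumulation statement in 3.1 and 5.5.1.

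The consequence is limited. No stopping rule, sample-size figure or response analysis depends on EKG, and the other data remain usable. The change is worth making because it is cheap and serves a primary objective.

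**What to change.** 1. Keep the Induction 1 pre-dose and first-dose EKGs.
2. Move the Consolidation 1 EKG to about 2 h post-dose at one of the weekly laboratory visits already required by 10.3 items 3b and 4b, during uninterrupted dosing. Record the crenolanib dose being taken.
3. Amend three places together: 10.3 item 2a, key a of Appendix IV part II, and the Consolidation table, whose on-treatment column now covers only the first day of crenolanib.
4. Reconcile the no-accumulation statements in 3.1 and 5.5.1 with the half-lives there and in 14.10 and the interval in 8.1.

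**Cost.** The number of EKGs is unchanged. The repeat first-dose EKG in consolidation is lost, along with its link to the Day 1 PK visit. That link is loose already, since the Consolidation 1 samples are pre-dose, 4 h and 8 h, with none at 2 h. The comparison with the Induction 1 baseline would span intervening chemotherapy and changes in concomitant drugs, so it would be descriptive only. Patients who never receive HiDAC would still have no EKG on continuous dosing. Adding one at the Induction 1 Day 15 PK visit would reach some of them, but it is an extra procedure and that visit exists only at selected sites.

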### III. Maintenance

Assessment	Maintenance 1-12	At time of progression or completion of study
Day within cycle	Day 1 ( $\pm$ 14 days)	
Prior/Concomitant medications, significant non-drug therapies	X a	X
Physical examination with ECOG PS	X a	X
Vitals and weight	X a	X
Assessment of adverse events, toxicities	X a	X
Hematology (CBC with differential)	X	X
Serum Chemistries (CMP with bilirubin, ALT/AST and creatinine)	X	X
Urine or serum Pregnancy test	Every 6 months while patient is on study	
Whole blood sample b		X
Bone marrow biopsy and aspirate c	Per SOC	X

**Key:**

a Day 1 and then per site standard schedule but no less frequent than every 2 months ( $\pm$ 1 month).

b Whole blood samples for translation research should be collected as defined in Section 11.

c Bone marrow biopsy and aspirate performed should have FLT3 testing and mutational status if available

## Appendix V. Common Terminology Criteria for Adverse Events; Version 4.03

Adverse Event	Cardiac Disorders				
	1	2	3	4	5
Anorexia Definition: A disorder characterized by loss of appetite.	Loss of appetite in eating habits	Oral intake altered without significant weight loss or malnutrition; oral nutritional supplements indicated	Associated with significant weight loss or malnutrition (e.g. inadequate oral caloric and/or fluid); tube feeding or TPN indicated	Life-threatening consequences; urgent intervention indicated	Death
Diarrhea Definition: A disorder characterized by frequent and watery bowel movements	Increase of <4 stools per day over baseline; mild increase in ostomy output compared to baseline	Increase of 4-6 stools per day over baseline; moderate increase in ostomy output compared to baseline	Increase of $\geq 7$ stools per day over baseline; incontinence; hospitalization indicated; severe increase in ostomy output compared to baseline; limiting self care ADL	Life-threatening consequences; urgent intervention indicated	Death
Fatigue Definition: A disorder characterized by a state of generalized weakness with a pronounced inability to summon sufficient energy to accomplish daily activities.	Fatigue relieved by rest	Fatigue not relieved by rest, limiting instrumental ADL	Fatigue not relieved by rest, limiting self care ADL	—	—
Nausea Definition: A disorder characterized by queasy sensation and/or the urge to vomit.	Loss of appetite without altering in eating habits	Oral intake decrease without significant weight loss, dehydration or malnutrition	Inadequate oral caloric or fluid intake; tube feeding, TPN, or hospitalization indicated	—	—
Vomiting Definition: A disorder characterized by the reflexive act of ejecting the contents of the stomach through the mouth.	1-2 episodes (separated by 5 minutes) in 24 hrs	3-5 episodes (separated by 5 minutes) in 24 hrs	$\geq 6$ episodes (separated by 5 minutes) in 24 hrs; tube feeding, TPN or hospitalization indicated	Life-threatening consequences; urgent intervention indicated	Death
Alanine aminotransferase increased Definition: A finding based on laboratory test results that indicate an increase in the level of alanine aminotransferase (ALT or SGPT) in the blood specimen.	>ULN-3.0 x ULN	>3.0-5.0 x ULN	>5.0-20.0 x ULN	>20.0 x ULN	—
Aspartate aminotransferase increased Definition: A finding based on laboratory test results that indicate an increase in the level of alanine aminotransferase (ALT or SGPT) in the blood specimen.	>ULN-3.0 x ULN	>3.0-5.0 x ULN	>5.0-20.0 x ULN	>20.0 x ULN	—
Blood bilirubin increased Definition: A finding based on laboratory test results that indicate an increase in the level of aspartate aminotransferase (AST or SGOT) in the blood specimen.	>ULN-1.5 x ULN	>1.5-3.0 x ULN	>3.0-10.0 x ULN	>10.0 x ULN	—

Adverse Event	Cardiac Disorders				
	Grade				
1	2	3	4	5	
Pleural effusion Definition: A disorder characterized by an amounts of fluid within the pleural cavity. Symptoms include shortness of breath, cough and market chest discomfort	Asymptomatic; clinical or diagnostic observations only; intervention not indicated	Symptomatic; intervention indicated (e.g. diuretics or limited therapeutic thoracentesis	Symptomatic with respiratory distress and hypoxia; surgical intervention including chest tube or pleurodesis indicated	Life-threatening respiratory or hemodynamic compromise; intubation or urgent intervention indicated	Death
Pericardial effusion Definition: A disorder characterized by fluid collection within the pericardial sac, usually due to inflammation.	—	Asymptomatic effusion size small to moderate	Effusion with physiologic consequences	Life-threatening consequences; urgent intervention indicated	Death
Edema face Definition: A disorder characterized by swelling due to excessive fluid accumulation in face tissues.	Localized facial edema	Moderated localized facial edema; limiting instrumental ADL	Severe swelling; limiting self care ADL	—	—
Edema limbs Definition: A disorder characterized by swelling due to excessive fluid accumulation in the upper or lower extremities.	5-10% inter-limb discrepancy in volume or circumference at point of greatest visible difference; swelling or obscuration of anatomic architecture on close inspection	>10-30% inter-limb discrepancy in volume or circumference at point of greatest visible difference; readily apparent obscuration of anatomic architecture; obliteration of skin folds; readily apparent deviation from normal anatomic contour; limiting instrumental ADL	≥30% inter-limb discrepancy in volume; gross deviation from normal anatomic contour, limiting self care ADL	—	—
Edema trunk Definition: A disorder characterized by swelling due to excessive fluid accumulation in the trunk area.	Swelling or obscuration of anatomic architecture on close inspection	Readily apparent obscuration of anatomic architecture; obliteration of skin folds; deadly apparent deviation from normal anatomic contour, limiting instrumental ADL	Gross deviation from normal anatomic contour; limiting self care ADL	—	—

